13.5. Appendix 5: Data Display Standards & Handling Conventions

13.5.1. Reporting Process

Software	

 The currently supported versions of SAS software 9.4 or higher will be used. 	
Reporting Area	
HARP Server	:\us1salx00259.corpnet2.com
HARP Compound	:\arwork\gsk3640254\mid208132\final_01
Analysis Datasets	

 Analysis datasets will be created according to CDISC standards (SDTM IG Version 3.2 & ADaM IG Version 1.1). 	
Generation of RTF Files	

RTF files will be generated for Tables, one RTF file per item. Listings will be generated in L10 format, and Figures will be generated in PDF format.
 
 	

13.5.2. Reporting Standards

General	

 The current GSK Integrated Data Standards Library (IDSL) will be applied for reporting, unless otherwise stated (IDSL Standards Location: https://spope.gsk.com/sites/IDSLLibrary/SitePages/Home.aspx): 
 4.03 to 4.23: General Principles 5.01 to 5.08: Principles Related to Data Listings 6.01 to 6.11: Principles Related to Summary Tables 7.01 to 7.13: Principles Related to Graphics 	
Formats	

 GSK IDSL Statistical Principles (5.03 & 6.06.3) for decimal places (DP's) will be adopted for reporting of data based on the raw data collected, unless otherwise stated. Numeric data will be reported at the precision collected on the eCRF. The reported precision from non eCRF sources will follow the IDSL statistical principles but may be adjusted to a clinically interpretable number of DP's. 	
Planned and Actual Time	

 Reporting for tables, figures and formal statistical analyses: 
 Planned time relative to dosing will be used in figures, summaries, statistical analyses and calculation of any derived parameters, unless otherwise stated. The impact of any major deviation from the planned assessment times and/or scheduled visit days on the analyses and interpretation of the results will be assessed as appropriate. Reporting for Data Listings: 
 Planned and actual time relative to study drug dosing will be shown in listings (Refer to IDSL Statistical Principle 5.05.1). Unscheduled or unplanned readings will be presented within the participant's listings. 	
Unscheduled Visits	

 Unscheduled visits will not be included in summary tables and/or figures. All unscheduled visits will be included in listings. 	
Descriptive Summary Statistics	

CONFIDENTIAL

208132

Continuous Data	Refer to IDSL Statistical Principle 6.06.1
Categorical Data	N, n, frequency, %
Graphical Displays	

 Refer to IDSL Statistical Principals 7.01 to 7.13. 	

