8.1.2. QTc Stopping Criteria

- The *same* QTcF correction formula *must* be used for *each individual participant* to determine eligibility for and discontinuation from the study. This formula may not be changed or substituted once the participant has been enrolled.
- The Baseline QTcF should be based on averaged QTcF values of triplicate electrocardiograms obtained over a brief recording period from the Day 1 pre-dose ECG.
- A randomized participant that develops an on-treatment QTcF >500 msec or an increase from baseline QTcF >60 msec should have two repeat unscheduled ECG's within 10 minutes. Using these triplicate ECGs, if the average QTcF >500 msec or an increase from baseline QTcF >60 msec, the subject will be withdrawn from the study.

Finally, this subject should have repeated unscheduled ECGs until their QTcF measurement returns to their original averaged QTcF value at Day 1 pre-dose.

See the SOA for data to be collected at the time of treatment discontinuation and follow-up and for any further evaluations that need to be completed.

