10.3.2. Primary Analyses

The final analysis will be performed after the completion of the study and final datasets authorization. Data will be listed and summarized according to GSK reporting standards, where applicable. Listings will be sorted by participant, period, day, and time, noting treatment; summaries will be presented by treatment, visit/day, and time. Unless stated otherwise, descriptive summaries will include n, mean, standard deviation (SD), coefficient of variation (%CV), median, minimum, and maximum, geometric mean with associated 95% confidence interval (CI), and %CVb for continuous variables, whereas n and percent will be used as summary statistics for categorical variables. Baseline or pre-dose assessment is the last available assessment prior to time of the first dose unless it is specified otherwise. If there are multiple assessments collected on the same scheduled time, the average of these assessments will be used. For tabulated safety summaries, only

the scheduled assessments will be included in the summary tables. Version 9.1 or higher of the SAS system will be used to analyze the data as well as to generate tables, figures, and listings. Complete details will be documented in the Reporting and Analysis Plan (RAP).

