
MONITORING:
 
For bilirubin or INR criteria:
 
 Repeat liver chemistries (include ALT, AST, alkaline phosphatase, bilirubin) and perform liver event follow up assessments within 24 hrs Monitor participants twice weekly until liver chemistries resolve, stabilize or return to within baseline A specialist or hepatology consultation is recommended 
For All other criteria:
 
 Repeat liver chemistries (include ALT, AST, alkaline phosphatase, bilirubin) and perform liver event follow up assessments within 24-72 hrs Monitor participants weekly until liver chemistries resolve, stabilize or return to within baseline 	
acetaminophen, herbal remedies, other over the counter medications.
 
 Record alcohol use on the liver event alcohol intake case report form (CRF) page 
For bilirubin or INR criteria:
 
 Anti-nuclear antibody, anti-smooth muscle antibody, Type 1 anti-liver kidney microsomal antibodies, and quantitative total immunoglobulin G (IgG) or gamma globulins. Serum acetaminophen adduct high performance liquid chromatography (HPLC) assay (quantifies potential acetaminophen contribution to liver injury in participants with definite or likely acetaminophen use in the preceding week [James, 2009]). NOTE: not required in China Liver imaging (ultrasound, magnetic resonance, or computerised tomography) and /or liver biopsy to evaluate liver disease: complete Liver Imaging and/or Liver Biopsy CRF pages.
---	---

1. Serum bilirubin fractionation should be performed if testing is available. If serum bilirubin fractionation is not immediately available, discontinue study treatment for that subject if ALT \geq 3xULN and bilirubin \geq 2xULN. Additionally, if serum bilirubin fractionation testing is unavailable, **record presence of detectable urinary bilirubin on dipstick**, indicating direct bilirubin elevations and suggesting liver injury.
2. All events of ALT \geq 3xULN and bilirubin \geq 2xULN (>35% direct bilirubin) or ALT \geq 3xULN and INR > 1.5, if INR measured which may indicate severe liver injury (possible 'Hy's Law'), **must be reported as an SAE (excluding studies of hepatic impairment or cirrhosis)**; INR measurement is not required and the threshold value stated will not apply to participants receiving anticoagulants

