2. SUMMARY OF KEY PROTOCOL INFORMATION

2.1. Changes to the Protocol Defined Statistical Analysis Plan

There were no changes or deviations to the originally planned statistical analysis specified in the protocol (Dated: 26/AUG/2019 Version: 208132/03).

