5.2. Baseline Definitions

For all endpoints (except as noted in baseline definitions) the baseline value will be the latest pre-dose assessment with a non-missing value, including those from unscheduled visits. If time is not collected, Day 1 assessments are assumed to be taken prior to first dose and used as baseline.

CONFIDENTIAL

208132

Parameter	Study Assessments Considered as Baseline		Baseline Used in Data Display
	Screening	Day 1 (Pre-Dose)	
Efficacy			
All efficacy endpoints	X	X	Day 1
Safety			
All laboratory, vital signs and ECG measurement endpoints	X	X	Day 1

Unless otherwise stated, if baseline data is missing no derivation will be performed and baseline will be set to missing.

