13.11.7. Safety Tables

Safety: Tables					
No.	Population	IDSL / Example Shell	Title	Programming Notes	Deliverable [Priority]
Adverse Events (AEs)					
3.1.	Safety	AE13	Adverse Events Overview		SAC
3.2.	Safety	AE1	Summary of All Adverse Events by System Organ Class and Preferred Term	ICH E3	HL, SAC
3.3.	Safety	AE5B	Summary of All Adverse Events by System Organ Class and Preferred Term and Maximum Grade	ICH E3	SAC
3.4.	Safety	AE3	Summary of Common ($\geq 5\%$) Adverse Events by Preferred Term	ICH E3	SAC
3.5.	Safety	AE15	Summary of Common ($\geq 5\%$) Non-serious Adverse Events by Preferred Term (Number of Subjects and Occurrences)	FDAAA, EudraCT	SAC
3.6.	Safety	AE1	Summary of All Drug-Related Adverse Events by System Organ Class and Preferred Term	ICH E3	HL, SAC
3.7.	Safety	AE5B	Summary of All Drug-Related Adverse Events by System Organ Class and Preferred Term and Maximum Grade	ICH E3	SAC
3.8.	Safety	AE1	Summary of Adverse Events of Special Interest		SAC
Serious and Other Significant Adverse Events					
3.9.	Safety	AE16	Summary of Serious Adverse Events by System Organ Class and Preferred Term (Number of Participants and Occurrences)	FDAAA, EudraCT	SAC
3.10.	Safety	AE1	Summary of Adverse Events Leading to Permanent Discontinuation of Study Treatment or Withdrawal from Study by System Organ Class and Preferred Term	IDSL	SAC

CONFIDENTIAL

208132

Safety: Tables					
No.	Population	IDSL / Example Shell	Title	Programming Notes	Deliverable [Priority]
Laboratory: Chemistry					
3.11.	Safety	LB1	Summary of Clinical Chemistry Data by Visit – Part 1	ICH E3	SAC
3.12.	Safety	LB1	Summary of Clinical Chemistry Data by Visit – Part 2	ICH E3	SAC
3.13.	Safety	LB1	Summary of Changes from Baseline in Clinical Chemistry Data by Visit – Part 1	ICH E3	SAC
3.14.	Safety	LB1	Summary of Changes from Baseline in Clinical Chemistry Data by Visit – Part 2	ICH E3	SAC
3.15.	Safety	LB18	Summary of Worst-Case Chemistry Grade Shifts from Baseline Grade – Part 1	ICH E3 Display only worst case post baseline visits.	HL, SAC
3.16.	Safety	LB18	Summary of Worst-Case Chemistry Grade Shifts from Baseline Grade – Part 2	ICH E3 Display only worst case post baseline visits.	HL, SAC
3.17.	Safety	LB17	Summary of Chemistry Laboratory Abnormalities of Potential Clinical Importance – Part 1		SAC
3.18.	Safety	LB17	Summary of Chemistry Laboratory Abnormalities of Potential Clinical Importance – Part 2		SAC

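### Worst-case and maximum safety tables exclude unscheduled values, so they can understate a participant's worst laboratory grade, vital sign or QTc category

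*SAP*

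**What the plan says.** SAP 13.5.2 sets one rule for all displays: "Unscheduled visits will not be included in summary tables and/or figures". The next line sends these data elsewhere: "All unscheduled visits will be included in listings". Protocol 10.3.2 says that, for safety tables, only "the scheduled assessments will be included in the summary tables". For withdrawn participants, SAP 13.7.1 lists everything but tabulates planned data only, unless otherwise specified. SAP 2.1 declares no departure from the protocol: "There were no changes or deviations to the originally planned statistical analysis specified in the protocol".

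SAP 13.11.7 then plans tables whose titles promise an extreme over the post-baseline period:

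- worst-case chemistry grade shifts (3.15, 3.16), with the programming note "Display only worst case post baseline visits";
- worst-case haematology grade shifts (3.25, 3.26);
- maximum QTc and maximum QTc increase (3.47 to 3.50);
- worst-case vital signs (3.54, 3.55).

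Tables that count a participant for any qualifying post-baseline value belong with them. These are potential clinical importance (3.17, 3.18, 3.27, 3.28), treatment-emergent toxicities (3.19, 3.20, 3.29, 3.30, 3.41, 3.42) and hepatobiliary abnormalities (3.39, 3.40).

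**The concern.** Restricting by-visit means and plots to scheduled visits is sound, because it keeps the denominators comparable. The same restriction does not suit a worst-case or maximum table, because the protocol orders extra tests for the participants with abnormal results. If the extra value is the more extreme one, the table reports the worst scheduled value under a title that says worst or maximum.

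Safety and tolerability is the first secondary objective. Both documents rule out formal safety analysis (Protocol 10.3.2.1, SAP 8), so the descriptive tables carry the result.

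**Working it through.** The plan gives no figure to reproduce. The check sets the rules side by side and then sizes one affected participant.

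**1. Does the protocol generate unscheduled values?** Yes, by three routes.

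- *QTc (Protocol 8.1.2).* A QTcF above 500 msec, or more than 60 msec above baseline, calls for two repeat ECGs within 10 minutes, which the protocol itself labels unscheduled. If the average confirms the finding, "this subject should have repeated unscheduled ECGs until their QTcF measurement returns" to the Day 1 pre-dose value.
- *Laboratory (Protocol 9.4.4).* Clinically significant abnormal results are repeated until they normalise, return to baseline or are no longer judged significant.
- *Liver (Protocol Appendix 7).* After a bilirubin or INR criterion, liver chemistry is repeated within 24 hours and then monitored twice weekly. After the other criteria, sites repeat the chemistry and "perform liver event follow up assessments within 24-72 hrs", then monitor weekly.

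A withdrawn participant has one planned follow-up visit, 7-14 days after stopping in Part 1 or 3-5 days in Part 2 (Protocol 8.2). Safety checks before that visit are largely unscheduled.

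**2. Does anything return these values to the extreme-value tables?** No. The note on 3.15 and 3.16 selects the worst visit but does not widen the set of visits. The maximum-QTc text in SAP 8.4.1 does not mention unscheduled ECGs. SAP 13.5.2 applies the sponsor's display standards unless otherwise stated, and its row on unscheduled visits states otherwise.

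**3. Could a same-visit repeat enter through the scheduled time point?** SAP 13.5.2 speaks of visits, so a confirmatory ECG taken within a scheduled visit might be thought eligible. Protocol 10.3.2 speaks of assessments, which excludes it. If it were admitted, SAP 13.6.1 would average it with the other measurements at that time point, and a mean lies below the maximum unless all the values are equal. Under either reading the table need not contain the maximum.

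**4. Where can a value be lost?** In two cases.

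- *The repeat is worse than the scheduled trigger.* For example, a scheduled QTcF is more than 60 msec above baseline but not above 500 msec, and a repeat exceeds 500 msec. The participant is placed too low in the maximum-QTc table.
- *The first abnormal value is itself unscheduled.* The participant is then not counted as abnormal.

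The clearest laboratory gap is in Part 1. The chemistry and haematology windows in SAP 13.3.1 include Day 11 and then resume at Day 18, leaving 17 - 12 + 1 = 6 days (Days 12-17) with no window. Clinic Visits 7 and 8 fall in that interval, but no chemistry or haematology is scheduled at them. A liver recheck 24-72 hours after a Day 11 sample falls on about Days 12 to 14, wholly inside the gap. If it shows a higher grade than Day 11 and the Day 18-24 value is lower, Table 3.15 reports too low a worst grade.

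**5. Size of one such participant.** Planned arm sizes are 6 (active) and 2 (placebo).

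- Active arm: 1/6 = 16.7 percentage points.
- Placebo arm: 1/2 = 50 percentage points.

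The documents give no rate for these events, so an expected number of misclassified participants cannot be calculated.

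**The case against.** The case for leaving the rule alone is substantial.

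- *It is pre-specified and consistent.* A reader might infer a conflict between protocol and SAP. There is none: both restrict safety tables to scheduled data.
- *The data are not lost.* Listings hold every unscheduled value. Display 3.51 lists QTc at all time points for participants above 500 msec or with an increase above 60 msec. Liver stopping events have their own summaries (3.37, 3.38). A reader might infer that an ALT beyond a stopping threshold would disappear, but those tables, the liver event form and Listing 27 would show it. A reader might also infer that no table uses data from unplanned contacts. SAP 5.1 does report adverse events from them, and a clinically significant abnormal laboratory or ECG result is an adverse event.
- *The trigger stays in the table.* A participant whose scheduled QTcF crosses an alert limit is counted. The later serial ECGs mainly document recovery, and Protocol 8.1.2 itself decides on an average.
- *Scheduled sampling is fairly dense.* Part 2 schedules chemistry on Days 1, 2, 3 or 4, 5 or 6, 7, 8 and 10-12, so many rechecks during dosing overlap a tabulated visit. Part 1 has ECGs on only five days, but these give 4 + 1 + 1 + 4 + 1 = 11 time points, 10 of them post-baseline.
- *The Part 1 gap belongs to the sampling schedule.* Without an unscheduled draw there is no value to add.

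A reader might also infer that peaks will usually be unscheduled; nothing in the documents supports that. Nor is it an error that baseline may use pre-dose values "including those from unscheduled visits". Baseline serves a different purpose, although the rule shows that the SAP can make an exception where it wants one.

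All of this limits the consequence. It does not put the highest value into a table titled maximum: listings and averaging leave the counts unchanged, and liver-event reporting covers one organ system.

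**Conclusion.** The point holds as a defect in a stated analysis rule. As written, the worst-case, maximum and any-time safety tables show the extreme among scheduled values only. Any error in the worst grade or category runs towards understatement, since omitting values cannot raise a maximum. This rests on reading SAP 13.5.2 and Protocol 10.3.2 as they stand, with no exception drawn from display standards that are not in the documents.

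The documents do not show that the error would be common, that a serious event would go unreported, or that any stopping decision or the primary analysis is affected. It is a modest problem of table accuracy, and it matters mainly because the arms are so small.

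**What to change.** In SAP 13.5.2, limit the exclusion to by-visit summaries and figures, and add a sentence such as: *Worst-case, maximum and any-time post-baseline summaries (laboratory grade shifts, treatment-emergent toxicities, potential clinical importance, hepatobiliary abnormalities, maximum QTc and QTc increase, worst-case vital signs) use all post-baseline values, scheduled and unscheduled, each taken individually and not averaged with repeats at the same time point; planned triplicate ECGs may still be averaged.* The worst-case urinalysis tables (3.35, 3.36) fall under the same rule and can be added to the list.

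Cross-refer from SAP 13.6.1, so that its averaging rule does not override the sentence, and from 13.7.1, so that withdrawn participants are treated alike. Record the change from Protocol 10.3.2 in SAP 2.1, which now reports none.

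The cost is a derivation flag in the analysis datasets, with no new data. Worst-case counts may become slightly less favourable. In Part 2, unscheduled values after Day 8 may be drawn on cART, as are the scheduled Visit 7 values already tabulated; a footnote can say so.

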13.5.3. Reporting Standards for Pharmacokinetic

Pharmacokinetic Concentration Data	
PC Windows Non-Linear (WNL) File	PC WNL file (CSV format) for the non-compartmental analysis by Clinical Pharmacology Modelling and Simulation function will be created according to PK One document (Standards for the Transfer and Reporting of PK Data using HARP). Note: Concentration values will be imputed as per GUI_51487
Descriptive Summary Statistics, Graphical Displays and Listings	Refer to IDSL PK Display Standards. Refer to IDSL Statistical Principle 6.06.1. Note: Concentration values will be imputed as per GUI_51487 for descriptive summary statistics/analysis and summarized graphical displays only.
NONMEM/Pop PK File	Not applicable.
NONMEM/PK/PD File	PK/PD file (CSV format) for the PK/PD analysis will be created according to the data specification detailed in Section 13.9 Pharmacokinetic/Pharmacodynamic Dataset Specification.
Pharmacokinetic Parameter Derivation	
PK Parameter to be Derived by Programmer	The following PK parameters will be derived by the Programmer: R_AUC, R_Cmax, R_C τ
Pharmacokinetic Parameter Data	
Is NQ impacted PK Parameters Rule Being Followed	Yes, refer to Standards for Handling NQ Impacted PK Parameters.
Descriptive Summary Statistics, Graphical Displays and Listings	Refer to IDSL PK Display Standards.
Units for PK Parameters	ug/mL for PK parameters; Original units (ng/mL) for listings, summary tables and figures of concentration-time data

13.6. Appendix 6: Derived and Transformed Data

13.6.1. General

Multiple Measurements at One Analysis Time Point

 • Mean of the measurements will be calculated and used in any derivation of summary statistics but if listed, all data will be presented. • Triplicate 12-lead ECGs will be recorded at each study-specified visit. Mean of the measurements will be calculated and used in any derivation of summary statistics but if listed, all data will be presented. • Participants having both High and Low values for Normal Ranges at any post-baseline visit for safety parameters will be counted in both the High and Low categories of “Any visit post-baseline” row of related summary tables. This will also be applicable to relevant Potential Clinical Importance summary tables.
Study Day

 • Calculated as the number of days from First Dose Date: 
 • Ref Date = Missing → Study Day = Missing • Ref Date < First Dose Date → Study Day = Ref Date – First Dose Date • Ref Date ≥ First Dose Date → Study Day = Ref Date – (First Dose Date) + 1

13.6.2. Study Population

Demographics
Age

Due to local privacy regulations, only the year of birth is recorded in the eCRF. The following algorithm will be used for imputation:
 
 • All dates of birth will be imputed using the 30th day of June. 
Completely missing dates of birth will remain as missing, with no imputation applied. Consequently, the age of the participant will not be calculated and will remain missing. In listings of demographic data, the year of birth as entered will be displayed.

Body Mass Index (BMI)

 • Calculated as $\text{Weight (kg)} / [\text{Height (m)}]^2$

13.6.3. Efficacy

Efficacy Parameters
Plasma HIV-1 RNA

 • If there are two values within a time window, the latest value will be used for summaries and analyses
CD4+ T-cell

 • If there are two values within a time window, the average value will be used for summaries and analyses

13.6.4. Safety

ECG Parameters
RR Interval

 IF RR interval (msec) is not provided directly, then RR can be derived as: 
 [1] If QTcB is machine read & QTcF is not provided, then: $RR = \left[\left(\frac{QT}{QTcB} \right)^2 \right] * 1000$ [2] If QTcF is machine read and QTcB is not provided, then: $RR = \left[\left(\frac{QT}{QTcF} \right)^3 \right] * 1000$ If ECGs are manually read, the RR value preceding the measurement QT interval should be a collected value THEN do not derive.
Corrected QT Intervals

 When not entered directly in the eCRF, corrected QT intervals by Bazett's (QTcB) and Fredericia's (QTcF) formulas will be calculated, in msec, depending on the availability of other measurements. IF RR interval (msec) is provided then missing QTcB and/or QTcF will be derived as:
$QTcB = \frac{QT}{\sqrt{\frac{RR}{1000}}} \qquad \qquad \qquad QTcF = \frac{QT}{\sqrt[3]{\frac{RR}{1000}}}$

Laboratory Parameters

 If a laboratory value which is expected to have a numeric value for summary purposes, has a non-detectable level reported in the database, where the numeric value is missing, but typically a character value starting with '<x' or '>x' (or indicated as less than x or greater than x in the comment field) is present, the number of significant digits in the observed values will be used to determine how much to add or subtract in order to impute the corresponding numeric value. 
 ○ Example 1: 2 Significant Digits = '< x' becomes x - 0.01 ○ Example 2: 1 Significant Digit = '> x' becomes x + 0.1 ○ Example 3: 0 Significant Digits = '< x' becomes x - 1

